21.2 Secondary Use of Data

The sponsor will reserve the right to secondary use of the study data. Secondary use of data refers to the use (including external provision) of collected data for purposes other than this study.

Major examples of secondary use of data are as follows:

- Use in other clinical studies
- Integrated analysis with relevant clinical studies
- Independent analysis by regulatory authorities and information sharing between regulatory authorities
- Use for epidemiological studies

22. ETHICS

22.1 Ethical Conduct of the Study

It is mandatory that all considerations regarding the protection of patients by complying with the protocol, the ICH GCP Guidelines, the ethical principles that have their origin in the Declaration of Helsinki, and all applicable regulatory requirements and grasping the latest information.

22.2 Approval by the Institutional Review Board

The study must be approved by an appropriately constituted IRB, as required by ICH guidelines (E6 Part 3). The conduct of this study must be reviewed and approved by the IRB and then approved by the head of the study site.

During the course of the study, the principal investigator will be responsible for obtaining continued review of the study. The timeframe for renewal is based on IRB requirements, but at least annually is required by regulations. At the end of the study, the IRB will be notified of the study completion and its outcome.

22.3 Procedure for Obtaining Informed Consent

Informed consent must be obtained in compliance with the guidelines provided in the Declaration of Helsinki, ICH Guideline (E6), and applicable regulatory requirements.

The principal investigator or subinvestigator will fully inform each patient of all pertinent aspects of the study in simple text.

Prior to the participation in the study, the informed consent form must be signed and dated by the patient and by the person giving an explanation about informed consent. A copy of the signed informed consent form will be given to the patient. The informed consent form approved by the IRB will be used.

By signing and dating the informed consent form prior to any study procedure specified in this protocol, the patient will be deemed to have consented to participate in the study.

The principal investigator will prepare an informed consent form based on a draft informed consent form provided by the sponsor. When the revision is necessary, the principal investigator will discuss with the sponsor, prepare the revised version, and use the version approved by the IRB.

23. STUDY ADMINISTRATIVE STRUCTURE

Details are described in the attachment.

25. APPENDICES

1000

For more information, contact the Office of the Vice President for Research and the Office of the Vice President for Student Affairs.

A 10x7 grid of black bars and dots. The bars are positioned in the first seven columns of each row. The heights of the bars vary across the rows, with the first row having the longest bars and the tenth row having the shortest. The dots are located in the last column of each row, positioned vertically below the bars. The grid is composed of thin black lines on a white background.

100

10 of 10 pages

	■	■	■	■	■	■	■
	■	■	■	■	■	■	■

100

For more information, contact the Office of the Vice President for Research and Economic Development at [contact] or [contact].

© 2019 Pearson Education, Inc.

Statistical Analysis Plan

Version 2.0

Name of investigational product	TAC-302
Study title	A Phase 2a Study of TAC-302 in Detrusor Underactivity Patients with Overactive Bladder
Protocol number	10054040
Date of preparation or revision	08 January 2020
Author	[REDACTED]

History of preparation and revision

Date	Author	Reason for preparation or revision
29 November 2019	[REDACTED]	Preparation of the first version
08 January 2020	[REDACTED]	Before unblinding, the analyses were changed based on the results of the blind review.

Date and signature

[REDACTED] Person in charge of statistical analysis	DD Month YYYY	
[REDACTED] Person responsible for statistical analysis	DD Month YYYY	
Taiho Pharmaceutical Co., Ltd. Statistical team leader	DD Month YYYY	

Changes in Statistical Analysis Plan

Version 1.0 (29 November 2019) to Version 2.0 (08 January 2020)

Item	Before change	After change	Reason for change
6.2.1 Table 6-3	< 65 years, ≥ 65 years	< 60 years, ≥ 60 years < 65 years, ≥ 65 years < 70 years, ≥ 70 years < 75 years, ≥ 75 years	The other categories have been added based on the results of the blind review.
7.3	Analysis of covariance with age (< 65 years, ≥ 65 years) as a covariate	By age (< 60 years and ≥ 60 years in males and < 70 years and ≥ 70 years in females), the above analysis excluding time course plots and analysis of covariance will be performed.	Separate age categories for men and women were specified based on the results of the blind review. Text was moved from 8.1.11.
8.1.11	Analysis of the primary endpoint and secondary endpoints (7.3 and 8.1.1 to 8.1.9)	Analysis of secondary endpoints (8.1.1 to 8.1.9)	Text was moved to 7.3.
	Secondary endpoints will be analyzed by sex (8.1.1 to 8.1.9). In analysis of covariance and analysis using an MMRM, sex will be excluded from the covariates.	Analysis will be performed as for analysis of secondary endpoints by sex (8.1.1 to 8.1.9). In analysis of covariance and analysis using an MMRM, values at baseline and age (< 60 years and ≥ 60 years in males and < 70 years and ≥ 70 years in females) will be used as covariates.	Separate categories for men and women were specified based on the results of the blind review.
8.3.1	≥ 65 years, < 65 years	≥ 65 years, < 65 years	A typographical error was corrected.
	The numbers of patients who experienced adverse events and the incidences of adverse events will be displayed. Similar analysis will be performed for adverse reactions. Similar analysis will also be performed by age (≥ 65 years and < 65 years).	The numbers of patients who experienced adverse events and the incidences of adverse events will be displayed. Similar analysis will be performed for adverse reactions. Similar analysis will also be performed by age (≥ 65 years and < 65 years). In addition, similar analysis will be performed by age (≥ 75 years and < 75 years).	Tabulation by age was added based on the results of the blind review.
	-	For each adverse event item, the numbers of patients who experienced adverse events and the incidences of adverse events will be displayed. Similar analysis will be performed for adverse reactions. Similar analysis will also be performed by age (≥ 65 years and < 65 years). In addition, similar analysis will be performed by age (≥ 75 years and < 75 years).	This was added to make the description more detailed. Tabulation by age (≥ 75 years and < 75 years) was added based on the results of the blind review.

	
For each adverse event item, the numbers of patients who experienced adverse events and the incidences of adverse events will be displayed by severity. Similar analysis will be performed for adverse reactions. Similar analysis will also be performed by age (≥ 65 years and < 65 years).
	
For each adverse event item, the numbers of patients who experienced adverse events and the incidences of adverse events will be displayed by severity. Similar analysis will be performed for adverse reactions.
	
This text was deleted because analysis by age will not be performed in analysis by severity.

--	--	--	---

TABLE OF CONTENTS

1. SCOPE AND OBJECTIVES	7
1.1 Primary Objective	7
1.2 Secondary Objectives.....	7
2. STUDY DESIGN AND TARGET SAMPLE SIZE	7
2.1 Study Design.....	7
2.1.1 Primary Endpoint.....	7
2.2 Target Sample Size.....	7
2.2.1 Target Sample Size.....	7
2.2.2 Rationale for the Sample Size.....	7
3. Data and Analysis Sets to Be Used for Statistical Analysis	8
3.1 Documents and Data Other Than Case Report Forms.....	8
3.2 Analysis Sets.....	9
4. METHODS OF STATISTICAL ANALYSIS	10
5. TIMING OF STATISTICAL ANALYSIS	10
6. ENDPOINTS AND COMMON ITEMS IN STATISTICAL ANALYSIS	11
6.1 Endpoints	11
6.1.1 Efficacy Endpoints.....	11
6.1.1.1 Pressure Flow Study (PFS)	11
6.1.1.2 Uroflowmetry.....	11

LIST OF ABBREVIATIONS AND DEFINITIONS OF TERMS

Abbreviations and terms used in the statistical analysis plan are defined below.

Abbreviation (term)	Description (definition)
BCI	Bladder Contractility Index
BMI	Body mass index
BOO	Bladder Outlet Obstruction
BVE	Bladder Voiding Efficiency
CIC	Clean Intermittent Catheterization
DU	Detrusor Underactivity
FAS	Full analysis set
ICH-E3 Guideline	"Guideline for Structure and Content of Clinical Study Reports" ¹⁾
IPSS	International Prostate Symptom Score
KHQ	King's Health Questionnaire
LOCF	Last Observation Carried Forward
MedDRA	Medical Dictionary for Regulatory Activities
MMRM	Mixed-effect Models for Repeated Measures
OAB	Overactive Bladder
OABSS	Overactive Bladder Symptom Score
PFS	Pressure Flow Study
PIP	Projected Isovolumetric Pressure
PPS	Per protocol set
free Q _{ave}	Average flow rate
free Q _{max}	Maximum flow rate
QOL	Quality of life
QTcF	QT corrected for heart rate by Fridericia's formula

1. SCOPE AND OBJECTIVES

This plan specifies the details of the statistical analysis plan for "A Phase 2a Study of TAC-302 in Detrusor Underactivity Patients with Overactive Bladder" (Protocol No. 10054040).

1.1 Primary Objective

To investigate the efficacy of TAC-302 in DU patients with OAB, using evaluation of the BCI (males) or PIP1 (females) at each time point as an indicator.

1.2 Secondary Objectives

- (1) To investigate the efficacy of TAC-302 in DU patients with OAB, using the changes in values including pressure flow study parameters, uroflowmetry parameters, BVE, IPSS or OABSS as indicators.
- (2) To investigate the efficacy of TAC-302 in DU patients with OAB compared to placebo.
- (3) To investigate the safety of TAC-302 in DU patients with OAB using data including the incidence of adverse events and adverse reactions as indicators.

2. STUDY DESIGN AND TARGET SAMPLE SIZE

2.1 Study Design

This study is a central-registration, multi-center, double-blind, placebo-controlled, randomized parallel-group comparative study to investigate the efficacy and safety of TAC-302 in detrusor underactivity patients with overactive bladder. This study is composed of a single-blind observation period, a double-blind treatment period, and a follow-up period.

2.1.1 Primary Endpoint

BCI ($P_{\text{det}}Q_{\text{max}} + 5 \times Q_{\text{max}}$) at Weeks 0 and 12 (males)
PIP1 ($P_{\text{det}}Q_{\text{max}} + Q_{\text{max}}$) at Weeks 0 and 12 (females)

2.2 Target Sample Size

2.2.1 Target Sample Size

75 patients to be enrolled in the treatment period (48 males and 27 females)

2.2.2 Rationale for the Sample Size

[REDACTED]

3. Data and Analysis Sets to Be Used for Statistical Analysis

3.1 Documents and Data Other Than Case Report Forms

A list of documents and data necessary for statistical analysis other than case report forms is shown in Table 3-1.

Table 3-1: Documents or Data Necessary for Statistical Analysis Other Than Case Report Forms

Item	Documents or data	Remarks
Attribution of patients	Flag of attribution of each patient to each analysis set	To identify the attribution of each patient to each analysis set.
	List of patients excluded from analysis sets and reasons for exclusion	To list patients excluded from analysis sets.
	UDS data subset and CIC status	To analyze by UDS data subset and by CIC status. The definition of UDS data subset is shown in 8.1.15.
Assignment information	Key code and allocation adjustment factors at the time of enrollment	To identify treatment groups and analyze using allocation adjustment factors.
Deviation information	Description of deviation and deviation flag	To provide a list of patients with deviations.
Conversion to MedDRA terms	Correspondence table between verbatim terms of adverse events and MedDRA terms	To tabulate the incidence of adverse events using standardized terms.
	Correspondence table between medical history and complication terms and MedDRA terms	To list medical history and complications using MedDRA terms.
Institutional reference value	Institutional reference values of laboratory values	To assess normal/abnormal laboratory values.
Drug name	Correspondence table between verbatim terms of concomitant drugs and WHO Drug Dictionary	To tabulate concomitant drugs in groups and specify the order.
Centralized assessment results	Results of centralized assessment of pressure flow study and uroflowmetry	For analysis of pressure flow study (only in patients enrolled in the treatment period) and uroflowmetry. However, for the results of pressure flow study in patients who are enrolled in the observation period and do not proceed to the treatment period, eCRF data (evaluation by the study site) will be used because there are no results of centralized assessment.
Efficacy evaluation	Efficacy evaluation data handling table	To additionally specify the handling of efficacy evaluation data

3.2 Analysis Sets

The analysis sets and their definitions are shown in Table 3-2. If there are patients for whom attribution to analysis sets is problematic based on factors other than the criteria shown below, handling of such patients will be determined by discussion between the sponsor and medical expert, etc. The primary efficacy analysis set will be PPS, and the primary safety analysis set will be all treated patients in the treatment period.

Table 3-2 Definition of Analysis Sets

Analysis Sets	Definition
Screening Patients	All patients who gave informed consent
All enrolled patients in the observation period	The set of all patients who were enrolled in the observation period
All enrolled patients in the treatment period	The set of all patients who were enrolled in the treatment period
All treated patients in the observation period	The set of patients enrolled in the observation period who took the investigational drug at least once
All treated patients in the treatment period	The set of patients enrolled in the treatment period who took the investigational drug at least once
Full Analysis Set(FAS)	The set of patients enrolled in the treatment period who took the investigational drug for the treatment period at least once and who had at least 1 efficacy endpoint measurement before the start of the treatment period and in the treatment period
Per Protocol Set(PPS)	The set of patients in the FAS, excluding patients who met any of the following criteria: (1) Being discovered to have a violation of the inclusion criteria (2) Being discovered to meet any of the exclusion criteria (criteria affecting efficacy evaluation) (3) A compliance rate for the treatment period of < 80% (4) Being administered prohibited concomitant drugs or prohibited concomitant therapy considered likely to influence efficacy evaluation (5) No evaluation of the primary endpoint at Week 12 of the treatment period

4. METHODS OF STATISTICAL ANALYSIS

The objective of the primary analysis is to evaluate the efficacy of TAC-302. As the primary analysis, summary statistics and the 95% confidence interval of BCI (males) or PIP1 (females) at Weeks 0 and 12 of the treatment period will be calculated at each evaluation time point by treatment group.

5. TIMING OF STATISTICAL ANALYSIS

Statistical analysis will be performed after completion of the study in all patients in this study. Before unblinding, preliminary examination (blind review) of the measurement of efficacy and safety, distribution of endpoints, relationship among items, and other aspects will be performed to make decisions regarding the handling of patient data, statistical analysis methods, and other points.

6. ENDPOINTS AND COMMON ITEMS IN STATISTICAL ANALYSIS

6.1 Endpoints

The efficacy and safety endpoints are defined below.

6.1.1 Efficacy Endpoints

6.1.1.1 Pressure Flow Study (PFS)

The volume at first desire to void, maximum bladder volume, bladder compliance, appearance of bladder involuntary contraction, and bladder volume up to appearance of bladder involuntary contraction will be evaluated based on the pressure flow study (filling phase). The detrusor pressure at start of voiding ($P_{det\ open}$), maximum detrusor pressure ($P_{det\ max}$), maximum flow rate (Q_{max}), average flow rate (Q_{ave}), maximum detrusor pressure at peak urine flow ($P_{detQ_{max}}$), duration of bladder contraction, voided volume, and post void residual will be evaluated based on the pressure flow study (voiding phase).

For the duration of bladder contraction, the duration of bladder contraction for urination including Q_{max} is defined as the duration of bladder contraction-1 and the duration of bladder contraction for all evaluable urinations during the voiding phase is defined as the duration of bladder contraction-2.

In the summary of patient backgrounds and the analysis by appearance of bladder involuntary contraction, patients judged to have bladder involuntary contraction at any of the evaluation time points (Weeks 0 and 12/at discontinuation) will be handled as those with bladder involuntary contraction. For the results at each evaluation time point (Weeks 0 and 12/at discontinuation), patients judged to have no bladder involuntary contraction at all time points will be handled as those without bladder involuntary contraction. Patients without data on presence/absence will be excluded from the analysis.

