2.3.2 Secondary Endpoints

2.3.2.1 Efficacy

- (1) PFS parameters (filling phase) [Evaluation time points: week 0, week 12]
 - Volume at first desire to void
 - Maximum bladder volume
 - Bladder compliance
 - Appearance of bladder involuntary contraction
 - Bladder volume up to appearance of bladder involuntary contraction
- (2) PFS parameters (voiding phase) [Evaluation time points: week 0, week 12]
 - Detrusor pressure at start of voiding ($P_{det\ open}$)
 - Maximum detrusor pressure ($P_{det\ max}$)
 - Maximum flow rate (Q_{max})

- Average flow rate (Q_{ave})
- Detrusor pressure at maximum flow ($P_{det}Q_{max}$)
- Duration of bladder contraction
- Voided volume
- Post void residual

(3) Uroflowmetry parameters [Evaluation time points: weeks 0, 4, 8, 12]

- Maximum flow rate (free Q_{max})
- Average flow rate (free Q_{ave})
- Voided volume
- Voiding time

(4) Post void residual measured by ultrasonography [Evaluation time points: at registration in observation period, weeks 0, 4, 8, 12]

(5) BVE [Voided volume / (voided volume + post void residual)] [Evaluation time points: weeks 0, 4, 8, 12]

Calculated from the voided volume measured by uroflowmetry and the post void residual measured by ultrasonography

(6) Change in IPSS score at weeks 4, 8, and 12 of the treatment periods relative to baseline (week 0)

- IPSS total score
- IPSS storage symptoms score
- IPSS voiding symptoms score
- IPSS QOL score

(7) Change in IPSS score at weeks 4, 8, and 12 of the treatment periods relative to baseline (week 0)

(8) Change in KHQ score (by domain) at week 12 of the treatment period relative to baseline (week 0)

(9) Change in bladder diary record data at weeks 4, 8, and 12 of the treatment periods relative to baseline (week 0)

- Average number of micturition per 24 hours
- Average number of urgency urinary incontinence episodes per 24 hours
- Average number of urinary urgency episodes per 24 hours
- Average voided volume per urination
- Average number of nocturnal urinations

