6.2 Common Items in Statistical Analysis

6.2.1 Patient Backgrounds

A list of patient backgrounds to be measured at enrollment is shown in Table 6-2. The details of categories when the background factors of continuous values among the background factors shown in Table 6-2 are divided by category are shown in Table 6-3.

Table 6-2 Background Factors

Item	Factor
Patient backgrounds	Sex, age, height, body weight, presence or absence of medical history, presence or absence of complications, race, ethnicity, and BMI
Disease characteristics	Timing of onset of lower urinary tract symptoms, presence or absence of pelvic visceral surgery, presence or absence of radiotherapy, presence or absence of drug therapy for the primary disease, bladder outlet obstruction index (males) ($P_{det}Q_{max} - 2Q_{max}$), prostate volume measurement (males), free Q_{max} , voiding time, voided volume (uroflowmetry), post void residual measured by ultrasonography, BVE (voided volume / [voided volume + post void residual] × 100), $P_{det}Q_{max}$, Q_{max} , BCI (males), PIP1 (females), IPSS total score, IPSS storage symptoms score, IPSS voiding symptoms score, IPSS (Q1, Q3, Q5, and Q6), presence or absence of CIC, presence or absence of bladder involuntary contraction, severity based on IPSS total score, severity based on IPSS QOLS score, and severity based on OABSS score

Table 6-3 Details of Categories

Category	Definition
Age category	< 60 years, ≥ 60 years < 65 years, ≥ 65 years < 70 years, ≥ 70 years < 75 years, ≥ 75 years
Race	Asian/Oriental, Other
Ethnicity	Japanese, .Other

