8.1.1 Pressure Flow Study (PFS) Parameters (Filling Phase)

For the volume at first desire to void, maximum bladder volume, bladder compliance, and bladder volume up to appearance of bladder involuntary contraction, the following analyses 1) to 5) will be performed. In addition, the analysis in 6) will be performed.

- 1) Summary statistics and 95% confidence intervals for the measured values at each evaluation time point (Weeks 0 and 12), and for the change and percentage change at Week 12 of the treatment period relative to baseline (Week 0), will be calculated.
- 2) Paired t-test for the measured values at baseline (Week 0) and Week 12 of the treatment period will be performed.
- 3) For the measured values at each evaluation time point (Weeks 0 and 12) and the change and percentage change from baseline (Week 0) to Week 12 of the treatment period, the 95% confidence interval for the difference between the placebo group and the TAC-302 group will be calculated.
- 4) For the change and percentage change from baseline (Week 0) to Week 12 of the treatment period, student's t test will be performed using the placebo group as the control.
- 5) Analysis of covariance of the change and percentage change from baseline (Week 0) to Week 12 of the treatment period will be performed using treatment group, baseline value, and age (< 65 years or \geq 65 years) as covariates, and the least squares means in each treatment group, and the difference in least squares mean between the placebo group and the TAC-302 group and its two-sided 95% confidence interval will be estimated.
- 6) The frequency of involuntary bladder contractions at each evaluation time point (Weeks 0 and 12) will be tabulated.

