8.1.12 Analysis by Severity Score

The following analyses will be performed. The same analyses will be performed by sex.

- Analyses of the primary and secondary endpoints excluding analysis of covariance/analysis using an MMRM and scatter plots (7.3 and 8.1.1 to 8.1.9) will be performed by IPSS total score at baseline (Week 0).
- Analyses of the primary and secondary endpoints excluding analysis of covariance/analysis using an MMRM and scatter plots (7.3 and 8.1.1 to 8.1.9) will be performed by IPSS QOL score at baseline (Week 0).
- Analyses of the secondary endpoints excluding analysis of covariance/analysis using an MMRM and scatter plots (7.3 and 8.1.1 to 8.1.9) will be performed by OABSS score at baseline (Week 0).

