8.1.14 Analysis by Appearance of Bladder Involuntary Contraction

The following analyses will be performed in the PPS. The same analyses will be performed by sex.

- Analyses of the primary and secondary endpoints (7.3 and 8.1.1 to 8.1.5) will be performed by appearance of bladder involuntary contraction. However, frequency tabulation of the appearance of bladder involuntary contraction and analysis of covariance/analysis using an MMRM in 8.1.1, 8.1.4, and 8.1.5 will not be performed.

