9.3 Patient Backgrounds

For each treatment group, summary statistics will be calculated or frequency tabulations will be performed to present appropriate summaries, depending on the data of each item of patient background. The same analysis will be performed by sex. Furthermore, for patients treated in the observation period and dropped out during the observation period, the same analysis will be performed in the subgroups of patients who did not meet the inclusion criterion (4) at enrollment in the treatment period and those who dropped out for other reasons.

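### The involuntary-contraction subgroups are defined partly from Week 12 results, so treatment can change who is in them

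*SAP*

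**What the plan says.** SAP 6.1.1.1 sets one rule for two uses: the summary of patient backgrounds and the analysis by appearance of involuntary contraction. Under it, "patients judged to have bladder involuntary contraction at any of the evaluation time points (Weeks 0 and 12/at discontinuation) will be handled" as positive. A patient counts as negative only if no contraction was judged present at any time point.

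The rule feeds two outputs:

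- **Background table.** SAP 6.2.1 states: "A list of patient backgrounds to be measured at enrollment is shown in Table 6-2". Presence or absence of involuntary contraction is one of the disease characteristics in that table.
- **Subgroup analysis.** SAP 8.1.14 states: "Analyses of the primary and secondary endpoints (7.3 and 8.1.1 to 8.1.5) will be performed by appearance of bladder involuntary contraction". It is run in the PPS and again by sex. Section 7.3 includes 95% confidence intervals for the difference between arms and Student's t-tests against placebo. The exclusion of covariance and MMRM analyses in 8.1.14 names only 8.1.1, 8.1.4 and 8.1.5, so the covariance analyses of 7.3 and 8.1.2 appear to run here too.

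The same variable is also an outcome. Protocol 2.3.2.1 lists "Appearance of bladder involuntary contraction" as a secondary efficacy endpoint evaluated at Weeks 0 and 12, and SAP 8.1.1 says: "The frequency of involuntary bladder contractions at each evaluation time point (Weeks 0 and 12) will be tabulated".

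Other clinical subgroups are fixed at baseline. In SAP 8.1.12 the analyses "will be performed by IPSS total score at baseline (Week 0"), with the same time point for the IPSS QOL and OABSS groupings. SAP 8.1.13 likewise uses post void residual at Week 0.

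**The concern.** Week 12 follows 12 weeks of randomised treatment. A patient with no contraction at Week 0 but one at Week 12 moves into the 'with' group. No patient can move the other way, because a Week 0 positive stays positive under the rule. If TAC-302 changes how often new contractions appear, the two arms lose different fractions of their Week 0-negative patients from the 'without' group and add different fractions to the 'with' group. Randomisation no longer protects the comparison inside either group, and a difference in BCI or PIP1 change could come from the sorting alone, in either direction.

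The background table has a related problem: an imbalance between arms in a table headed as measured at enrollment could have been produced by treatment. One part of this needs no drug effect. SAP 9.3 repeats the background summary for observation-period dropouts, including "patients who did not meet the inclusion criterion (4) at enrollment in the treatment period". They have at most a Week 0 study, whereas treated patients generally have two chances to be positive.

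**Working it through.** **What the documents supply.** The plan states no figure for this subgroup, so there is none to reproduce. Target enrolment is 48 men and 27 women (SAP 2.2.1), allocated 2:1 (Protocol 3), which gives 32:16 men and 18:9 women. The PPS requires a Week 12 primary endpoint evaluation (SAP 3.2), so patients in 8.1.14 have had a Week 12 pressure flow study that can change their group.

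**What is assumed.**

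- Proportion positive at Week 0: p = 0.5 in both arms.
- New contraction among Week 0 negatives: nT on TAC-302 and nP on placebo, each 0.1 to 0.4.
- Mean BCI change in newly positive minus still-negative patients: d, from -1 to +1 SD.
- No drug effect on BCI change, the same mean change in Week 0 positives and Week 0 negatives, and no selection into the PPS.

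**Spurious difference, TAC-302 minus placebo.** Set the mean change of all Week 0 negatives to 0. Those who stay negative then average -n·d, and the newly positive average (1-n)·d.

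- 'Without' group: (nP - nT)·d
- 'With' group: f(nT) - f(nP), where f(n) = (1-p)·n·(1-n)·d / [p + (1-p)·n]

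With nT = 0.1 and d = -1:

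| nP | 'Without' (SD) | 'With' (SD) |
|---|---|---|
| 0.1 | 0 | 0 |
| 0.2 | -0.10 | +0.05 |
| 0.3 | -0.20 | +0.08 |
| 0.4 | -0.30 | +0.09 |

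For the last row, f(0.1) = -0.045/0.55 = -0.082 and f(0.4) = -0.12/0.70 = -0.171, a difference of +0.09. Signs reverse for d = +1 or if the two rates are swapped. With d = 0 both columns are 0.

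**Precision, men, nT = 0.1 and nP = 0.1 to 0.4.** SE = sqrt(1/a + 1/b) at expected counts a and b.

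- 'Without': TAC-302 32 × 0.5 × 0.9 = 14.4; placebo 16 × 0.5 × (0.9 to 0.6) = 7.2 to 4.8. SE = 0.46 to 0.53 SD.
- 'With': 17.6 versus 8.8 to 11.2. SE = 0.41 to 0.38 SD.
- Week 0 definition, either group: 16 versus 8. SE = 0.43 SD.

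For women, the 'without' group holds 8.1 versus 4.05 to 2.7 patients, with SE = 0.61 to 0.70 SD. The largest spurious difference in the 'without' group, 0.30 SD, is therefore below one SE for either sex.

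**False-positive rate.** In simulated trials of 32:16 men with a nominal 5% t-test, the 'without' group at d = -1 and 10% versus 40% rejects in about 8% (7.7% to 8.5% across simulation set-ups). At d = -0.5 and 10% versus 20% it stays at 5%. The 'with' group stays below 6%. Under the Week 0 definition the mean difference is about zero.

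**A second model.** Correlating endpoint change with liability to Week 12 contraction (|rho| 0.3 to 0.5), with new-contraction rates of 10% on TAC-302 and 30% on placebo and Week 0 prevalence 0.3 to 0.7, gives about 0.09 to 0.15 SD in 'without' and 0.02 to 0.08 SD in 'with'. Grouping by Week 0 gives 0.00 SD in every scenario.

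**Background table.** With 50% positive in both arms at Week 0, the table would read 0.5 + 0.5 × 0.1 = 55% on TAC-302 and 0.5 + 0.5 × (0.2 to 0.4) = 60% to 70% on placebo.

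**The case against.** The strongest reply is about weight. This is one supplementary subgroup analysis in a phase 2a study with no multiplicity control. The primary analysis (SAP 7.1) is by-arm summary statistics and does not use the grouping. The size rests entirely on assumed rates, and 0.30 SD is the extreme corner of the range. Contraction frequency is tabulated separately at Weeks 0 and 12, so a reader can still see the true Week 0 balance. Section 6.1.1.1 names the background summary openly, which leaves mainly a labelling mismatch with 6.2.1. In 8.1.14 the discontinuation route hardly matters, because the PPS excludes patients without a Week 12 primary endpoint evaluation. Not every other grouping is tied to Week 0 either: no time point is stated for catheterization status, and the UDS data subset comes from a data review.

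Those points stand, and they limit how much this matters. Two further arguments do not remove it. The rule could be meant as a patient trait seen on either of two examinations, but the SAP gives no such reason, and that reading would still condition on a result obtained after randomisation. Finalising the plan before unblinding prevents a data-driven choice; it does not make a Week 12 result a baseline one.

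**Conclusion.** The concern holds. As written, the grouping conditions a between-arm comparison on a post-randomisation outcome and reports that outcome as an enrollment characteristic. Bias requires both a difference between arms in new contractions and a link between contraction and the endpoint; the documents do not say whether either exists. Under the assumed ranges it is at most 0.30 SD in the 'without' group and 0.09 SD in the 'with' group, in either direction. In groups this small it would be hard to separate from chance, but the within-subgroup tests and intervals would not have a clean interpretation. The change should be made; the trial's main result does not depend on it.

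**What to change.** In SAP 6.1.1.1, Table 6-2 and 8.1.14, define presence or absence from the Week 0 pressure flow study alone, and exclude patients with no Week 0 result. This also settles how to class a patient who is negative at Week 0 and has no later result, which the present rule leaves open. Use the central assessment for patients enrolled in the treatment period. For those who did not proceed, SAP 3.1 already provides that "eCRF data (evaluation by the study site) will be used because there are no results of centralized assessment", so the dropout summaries in 9.3 keep this characteristic. Week 12 contraction remains an outcome under 8.1.1. If an ever-positive grouping is wanted, keep it as a descriptive table labelled post-baseline, with no between-arm tests or intervals. Add this subgroup to the list in 11.8.

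The cost is SAP wording; the Week 0 study is already scheduled. On the assumptions above, for men, the 'with' group falls from 17.6 versus 8.8 to 11.2 patients to 16 versus 8, and its SE goes from 0.38 to 0.41 SD to 0.43 SD. The 'without' group grows to 16 versus 8, and its SE improves from 0.46 to 0.53 SD to 0.43 SD. Selection into the PPS after randomisation remains under either rule.
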